## Study Summary

Title	Combination Ibrutinib and Rituximab for Treatment of Chronic Graft-Versus-Host Disease Following Allogeneic Stem Cell Transplant
Short Title	Ibrutinib and Rituximab for Steroid-Refractory or Dependent Chronic GVHD
Protocol Number	D17120
Phase	Phase 1/2
Methodology	Open label, Within-Subject Dose-Escalation Study
Study Duration	2 years (patients will be followed after 6 months for survival only)
Study Center(s)	Single center
Objectives	To determine the safety and efficacy of Ibrutinib and Rituximab combination therapy for steroid-refractory or -dependent chronic GVHD following allogeneic stem cell transplant.
Number of Subjects	15
Diagnosis and Main Inclusion Criteria	Steroid refractory or dependent chronic graft-versus-host disease (diagnosis to be based on histologic sampling and/or via clinical criteria; see Attachments) > 18 years old Karnofsky Performance Status 60 or greater

Study Product, Dose, Route, Regimen	
Within-Subject Dose-Escalation Format:
 
 
-The first 5 subjects will receive treatment as follows: 
 
-Ibrutinib 140 mg po once daily
 
-Rituximab 375 mg/m^2 IV weekly x4
 
 
 
-Adverse events will be defined as per the NCI Common Terminology Criteria for Adverse Events (CTCAE) 
 
-if no adverse events <math>\geq</math> non-hematologic grade 3 or <math>\geq</math> hematologic grade 4 are noted after 1 week at 140 mg daily, the Ibrutinib dose schedule will be increased to 280 mg daily
 
-if no adverse events <math>\geq</math> non-hematologic grade 3 or <math>\geq</math> to hematologic grade 4 are noted after 1 week at 280 mg daily, the Ibrutinib dose schedule will be increased to 420 mg daily
 
- the potential exists for a 2nd weekly x4 Rituximab course 8 weeks after initial Rituximab therapy, if no response or an incomplete response is noted
 
 
 
 
Expansion cohort:
 
 
- following accrual of the 5 initial subjects, an additional 10 subjects will be accrued, with dosing to be informed by the results of the within-subject dose escalation cohort
 

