### 5.1.1 Details of the Treatment Regimen

**Initial cohort (first 5 patients accrued) will be treated as follows:**

Ibrutinib 140 mg po once daily with

Rituximab 375 mg/m^2 IV weekly x4 (with pre-medications and infusion procedure as per standard protocol)

Rituximab Pre-medications: Acetaminophen 650 mg po; Diphenhydramine 25 mg po/IV; Dexamethasone 20 mg IV

If no adverse events  $\geq$  nonhematologic grade 3 or  $\geq$  hematologic grade 4 are noted after 1 week at 140 mg daily, the Ibrutinib dose schedule will be increased to 280 mg daily

If no adverse events  $\geq$  nonhematologic grade 3 or  $\geq$  hematologic grade 4 are noted after 1 week at 280 mg daily, the Ibrutinib dose schedule will be increased to 420 mg daily.

If grade  $\geq$  3 non-hematologic toxicity and/or grade 4 hematologic toxicity are noted, a dose de-escalation to the prior dose level will be made. Resumption of treatment at this dose level may begin once Ibrutinib toxicity has improved to the grade 1 (or baseline) level.

If a  $\geq$  nonhematologic grade 3 or  $\geq$  hematologic grade 4 adverse event is noted in any one of the 5 subjects at the 140 mg dose level, a thorough review of this AE will be undertaken, and if deemed causative, treatment for that subject will be discontinued.

If a  $\geq$  nonhematologic grade 3 or  $\geq$  hematologic grade 4 adverse event is noted in  $>2$  of the 5 subjects at the 140 mg dose level, the study will be discontinued.

If a  $\geq$  nonhematologic grade 3 or  $\geq$  hematologic grade 4 adverse event is noted in a subject at the 280 mg dose level, the subject will then be dropped back to the prior dose level or treatment for that subject will be discontinued.

If a  $\geq$  nonhematologic grade 3 or  $\geq$  hematologic grade 4 adverse event is noted in a subject at the 420 mg dose level, the subject will then be dropped back to the prior dose level or treatment for that subject will be discontinued.

If therapy for 2 or more subjects at either the 280 mg or 420 mg dose level requires discontinuation, per the above parameters, no further escalation to those dose levels will be attempted for future patients.

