**Expansion cohort (additional 10 patients accrued) will be treated as follows:**

Ibrutinib 420 mg po once daily with

Rituximab 375 mg/m^2 IV weekly x4

If, based on above toxicity criteria, the Ibrutinib 420 mg daily dose schedule has been discontinued, then 280 mg po once daily will be the expansion cohort dose schedule

If, based on above toxicity criteria, the Ibrutinib 280 mg daily dose schedule has been discontinued, then 140 mg po once daily will be the expansion cohort dose schedule

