**Visit 2 at 1-2 weeks from initiation of the combination therapy (sooner as clinically indicated)**

- i. A subject will be assessed for:
  - a. Medical history
  - b. Physical examination, including height and weight
  - c. Blood and urine tests, as clinically indicated
  - d. Additional organ function, as clinically indicated
- ii. Patients will be followed at no longer than two-week intervals over the first six weeks on trial, more frequently as clinically indicated. Note: participants in the dose escalation portion of the protocol will be followed via weekly visits, more frequently as indicated.

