### Expansion cohort (additional 10 patients accrued) will be treated as follows:

Ibrutinib 420 mg po once daily with

Rituximab 375 mg/m^2 IV weekly x4

If, based on above toxicity criteria, the Ibrutinib 420 mg daily dose schedule has been discontinued, then 280 mg po once daily will be the expansion cohort dose schedule

If, based on above toxicity criteria, the Ibrutinib 280 mg daily dose schedule has been discontinued, then 140 mg po once daily will be the expansion cohort dose schedule

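### The rule closing 280 mg or 420 mg covers only future patients, so an enrolled subject still in the two-week ramp could be escalated into a level just closed (minor safety wording)

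*Combined protocol and SAP*

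**What the plan says.** Only the initial cohort of five subjects escalates. Each starts ibrutinib at 140 mg with weekly rituximab. If no qualifying adverse event (non-hematologic grade 3 or worse, hematologic grade 4 or worse) occurs, section 5.1.1 moves the subject up in two steps:

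- After the first week: if no such events "are noted after 1 week at 140 mg daily, the Ibrutinib dose schedule will be increased to 280 mg daily".
- After the second week: if none is seen at 280 mg, "the Ibrutinib dose schedule will be increased to 420 mg daily".

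The Study Summary and section 8.5 carry the same two steps.

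The closing rule, identical in 5.1.1 and 8.5, is triggered as follows: "If therapy for 2 or more subjects at either the 280 mg or 420 mg dose level requires discontinuation, per the above parameters". Its consequence is that "no further escalation to those dose levels will be attempted for future patients".

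The expansion cohort of ten starts at a fixed dose, 420 mg by default. If "the Ibrutinib 420 mg daily dose schedule has been discontinued", "then 280 mg po once daily will be the expansion cohort dose schedule". A parallel sentence steps down to 140 mg if 280 mg has been discontinued.

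**The concern.** A rule that closes a dose level for toxicity should protect everyone who has not yet reached that level. This one names only future patients. Within the initial cohort that phrase naturally means subjects not yet enrolled, so it leaves out a subject who is already taking 140 mg or 280 mg when the level closes. For that subject the only operative instruction is the escalation step, whose sole condition is a clean week.

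Following the text exactly would therefore raise a subject to a dose at which two others have just had to stop treatment. If 280 mg is the level that closes, a subject already tolerating 280 mg would go on to 420 mg. Safety is the primary objective, and section 1.5 explains that the escalation format was chosen because the earlier combination data came from patients who had not had an allogeneic transplant. The closing rule is part of that protection.

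**Working it through.** **Text check.** The question is whether any provision holds an enrolled subject below a closed level.

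| Provision | Effect on an enrolled subject still in the ramp |
|---|---|
| Escalation steps (Study Summary, 5.1.1, 8.5) | Directs an increase after a clean week; no condition that the level is open |
| Closing rule (5.1.1, 8.5) | Names future patients only |
| Expansion-cohort dose (5.1.1, 8.5) | Speaks of a discontinued schedule, but sets only the expansion dose |
| Individual drop-back rules (5.1.1, 8.5) | Act only after that subject has had a qualifying event |
| Physician's power to stop the study (4.4.1) | General discretion, not a dose-level hold |
| Monitoring committee (10.2) | Meets quarterly, against a two-week ramp |

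No provision staggers the first five subjects, so ramps can overlap. The ramp lasts 1 + 1 = 2 weeks. Once two subjects have discontinued, at most 5 − 2 = 3 can be exposed.

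**Size.** The plan gives no figure to reproduce. All rates below are assumptions.

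*Chance that the rule is triggered.* If each of the five discontinues at 420 mg with probability q, P(2 or more) = 1 − (1 − q)^5 − 5q(1 − q)^4:

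- q = 0.10: 1 − 0.5905 − 0.3281 = 0.081
- q = 0.20: 1 − 0.3277 − 0.4096 = 0.263

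*Chance that someone is in the ramp when 420 mg closes.* Simulation, 400,000 runs per setting:

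- 15 subjects enrol uniformly over 18 or 24 months and the first five form the initial cohort. The fifth enrols on average at 5/16 of the period, about 5.6 or 7.5 months.
- 280 mg starts on day 7 and 420 mg on day 14.
- Discontinuation at 420 mg has probability q, timed uniformly over the first W weeks at that dose. The second discontinuation closes the level.
- Each ramp week has probability b of an event that blocks escalation.
- A run counts if, at closure, any initial subject is within 14 days of starting and has both ramp weeks clean.

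Results in percent, ranges over 18 and 24 months:

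| W | b=0, q=10% | b=0, q=20% | b=10%, q=10% | b=10%, q=20% | b=20%, q=10% | b=20%, q=20% |
|---|---|---|---|---|---|---|
| 4 weeks | 1.17–1.45 | 4.07–4.99 | 0.64–0.78 | 2.30–2.77 | 0.32–0.40 | 1.20–1.46 |
| 12 weeks | 0.87–0.97 | 3.07–3.44 | 0.49–0.51 | 1.77–1.93 | 0.24–0.27 | 0.92–0.97 |
| 24 weeks | 0.49–0.55 | 1.81–1.99 | 0.29–0.30 | 0.99–1.08 | 0.14–0.15 | 0.51–0.57 |

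The b = 0 columns are upper figures, because they assume that every ramp week is clean.

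*Given that 420 mg closes.* Dividing by the trigger probability at b = 0 gives 0.49/8.15 = 6% at the low end and 4.99/26.27 = 19% at the high end. The event is uncommon mainly because closure is uncommon.

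*Closure of 280 mg.* Discontinuation has probability r, timed uniformly over days 7–14. The count is of any initial subject on days 0–14 who does not discontinue at 280 mg:

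- r = 5%: 0.35–0.45% (subject at 140 mg 0.19–0.24%, at 280 mg 0.18–0.23%)
- r = 10%: 1.29–1.65% (at 140 mg 0.69–0.88%, at 280 mg 0.65–0.85%)

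In about half of these cases the subject is already at 280 mg and would go up to 420 mg. These runs leave out later discontinuations at 280 mg after drop-back from 420 mg. They also do not exclude a 140 mg subject whose own event would block escalation.

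*Faster accrual.* If the five enrol over 1 to 12 months, q is 20% or 40%, and discontinuation falls on days 14–56, the chance given closure is about 8–30%. Multiplied by the trigger probability, this is 0.263 × 0.076 = 2% at the low end and 0.663 × 0.298 = 20% at the high end. The top value needs 40% discontinuation and all five enrolled in about three months. Nothing in the documents supports either assumption, so these figures are a bound rather than an estimate.

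**The case against.** The strongest reply is that the protective reading fits the document better. Only the initial cohort escalates, so a bar on further escalation can concern only those five. The expansion text refers to a schedule that has been discontinued on the same toxicity criteria, which is level-wide language, and a sensible investigator would probably hold the dose. This stands as evidence of intent. It does not change what the closing sentence says: the words about future patients limit it, and the expansion sentences direct only the expansion dose.

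The second reply is that harm is already contained. In the escalation phase "participants in the dose escalation portion of the protocol will be followed via weekly visits". Serious adverse events must reach the principal investigator within 24 hours (8.3.1) at what is a single center, and that investigator is responsible for safety oversight (10.1). Section 8.3.2 foresees protocol changes made without prior IRB review to remove an immediate hazard. Section 1.5 cites data supporting 420 mg after transplant. These points are correct and are why the matter is minor. But they limit harm or permit a departure from the text; they do not supply the missing rule. Two discontinuations would also be new information about the combination in this population.

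The third reply is that a cheap edit is not thereby an important one. That is fair, and the point is not put higher than a small correction to a stopping rule.

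**Conclusion.** The concern holds as a minor safety correction. It is limited to enrolled initial-cohort subjects who have not yet reached the closed level, or who would go above it. Subjects already tolerating a closed level remain under the individual drop-back rules.

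Counting only subjects who would in fact be increased (a 10–20% chance of a blocking event per ramp week), the probability for 420 mg is about 0.1–0.8% at a 10% discontinuation rate and 0.5–2.8% at 20%. These figures rest on assumed accrual, discontinuation and timing. The textual finding does not depend on them.

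**What to change.** In 5.1.1 and 8.5, replace the end of the closing sentence with:

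> *no further escalation to that dose level or any higher level will be made for any subject, whether already enrolled or future; a subject below it goes no higher than the highest level still open.*

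The reference to any higher level is needed so that a subject at 280 mg is not moved to 420 mg after 280 mg closes. The last clause lets a subject at 140 mg still go to 280 mg when only 420 mg has closed. Subjects already tolerating a closed level stay under the existing drop-back rules, with no escalation above it. The separate escalation sentences and the Study Summary can stay as they are, because the closing sentence would then expressly govern every subject.

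The change touches one sentence in two places. It needs no extra patients, visits or procedures, and leaves sample size, significance level and power unchanged. The one scientific cost is possibly fewer initial-cohort subjects with data at a closed or higher level.

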**Expansion cohort (additional 10 patients accrued) will be treated as follows:**

Ibrutinib 420 mg po once daily with

Rituximab 375 mg/m^2 IV weekly x4

If, based on above toxicity criteria, the Ibrutinib 420 mg daily dose schedule has been discontinued, then 280 mg po once daily will be the expansion cohort dose schedule

If, based on above toxicity criteria, the Ibrutinib 280 mg daily dose schedule has been discontinued, then 140 mg po once daily will be the expansion cohort dose schedule

#### **Duration of therapy:**

Ibrutinib -> 420 mg daily (or adjusted dose) will continue until progression of cGVHD or development of significant side effects.

Rituximab -> there is the potential for a 2nd weekly x4 Rituximab course 8 weeks after initial therapy, if no response or an incomplete response is noted.

### 5.1.2 Baseline Assessment and Follow-Up Determination of Therapeutic Response

The baseline and follow-up assessments of protocol participants will be done utilizing NIH criteria, as outlined in the 2014 NIH Consensus Development Project Report on Criteria for Clinical Trials in Chronic Graft-versus-Host Disease (26) and Measuring Therapeutic Response in Chronic Graft-versus-Host Disease (27).

#### **See Attachments:**

**Attachment 1:** Chronic GVHD Scoring Assessment – Clinician (26)

**Attachment 2:** Response Determination Table for Chronic GVHD Clinical Trials (27)

The timeframe for assessments will be as follows: baseline (pre-treatment); 6 weeks, 3 months and 6 months after initiation of therapy.

The mode of assessment will include the following (to be undertaken by a limited number of team members who will do these assessments, so as to ensure consistency and minimize subjectivity).

## **5.2 Supportive Care Recommendations**

**5.2.1 Infectious prophylaxis** will include fluconazole, acyclovir and both PJP and encapsulated organism prophylaxis (recommendations from DHMC SOP addressing antimicrobial prophylaxis following hematopoietic transplantation, and adapted from BBMT 2009; 15: 1143). The following are recommended:

Fluconazole 400 mg po daily

Acyclovir 800 mg po bid

TMP-SMX or alternative PJP prophylaxis

TMP-SMX or alternative encapsulated organism prophylaxis (during steroid and other GVHD therapy).

**5.2.2 CMV PCR monitoring** - using standard guidelines and the DHMC SOP addressing monitoring of post-transplant CMV status, it is recommended that CMV PCR be tested during active cGVHD therapy, weekly if prior to post-transplant day +100 and prior to 1 year post-transplant timeframe if previous CMV activation was documented. If after day +100 in the absence of previous CMV reactivation, then CMV PCR monitoring should be done at two-week intervals. Monitoring will continue while the patient remains on immune suppression, as clinically indicated. Treatment for a positive result will be done according to standard guidelines, as outlined in the DHMC SOP regarding pre-emptive CMV therapy.

**5.2.3 EBV monitoring** - using standard guidelines and the DHMC SOP addressing monitoring of post-transplant EBV status, it is recommended that EBV PCR testing after transplant be considered between days +30 to 100, as clinically indicated, based on the presence of fever, adenopathy or other signs or symptoms of infection or post-transplant lymphoproliferative disorder (PTLD). PCR monitoring should be done periodically after this timeframe, following evidence of reactivation, including during active cGVHD treatment with steroids and/or other immunosuppressive agents. Treatment for a positive result will be done according to standard guidelines as outlined in the DHMC SOP for Management of Viral Infections after Hematopoietic Stem Cell Transplant.

## **5.3 Method for Assigning Subjects to Treatment Groups**

Open label single arm study.

## **5.4 Preparation and Administration of Study Drug**

Ibrutinib will be mailed to a participant's address.

Rituximab will be administered weekly in the infusion suite at the Hematology Outpatient Clinic, Norris Cotton Cancer Center (NCCC), Dartmouth-Hitchcock Medical Center (DHMC).

Rituximab will be prepared and dispensed through the Investigational Pharmacy, DHMC.

For more information:

Investigational Pharmacy, NCCC, DHMC

Contact [contact]

## **5.5 Subject Compliance Monitoring**

Each study subject will be assessed weekly from initiation of the study. A drug administration log for Ibrutinib will be utilized (including date, time and dose taken) and maintained, and patients will be queried about regular administration of Ibrutinib, as recorded in this log. Rituximab administration will be monitored through the electronic medical record (EMR) system.

## **5.6 Prior and Concomitant Therapy**

### **5.6.1 Restricted and Allowable Concomitant Medications**

1. History of treatment with a tyrosine kinase inhibitor (eg, imatinib) or other significant CYP4A inhibitor within 2 weeks of enrollment is NOT allowed.
2. History of standard-dose Rituximab therapy within 6 months of study enrollment is NOT allowed.
3. Pre-transplant use of Ibrutinib for indications other than cGVHD (eg, lymphoma therapy) IS permitted.
4. Concomitant use of corticosteroids for cGVHD after transplant, prior to and during this study, IS permitted and anticipated (with no dose change allowed for a period of at least 14 days prior to enrollment).
5. Concomitant use of other immunosuppressive therapies prior to and during this study IS also permitted (with no dose change allowed for a period of at least 14 days prior to enrollment).
6. Doses of concomitant steroids and other immunosuppressants may be tapered during the study, as clinically feasible.
7. Study subjects may receive prophylactic antimicrobials, based on post-transplant status.

### **5.7 Treatment Discontinuation and Subsequent Therapy**

If there is progression of disease on evaluation at 6 weeks, 3 months or 6 months, the patient will be considered for other secondary therapies, depending on the severity of the cGVHD and his/her overall clinical status. Other commonly used secondary therapies include Tacrolimus/sirolimus, Mycophenolate mofetil, extracorporeal photophoresis (ECP), JAK1/2 inhibitors and other monoclonal antibodies. Pulsed steroid therapy may also need to be considered in an effort to control the degree of GVHD as a purely temporary measure (ie, “bridge” to secondary therapy).

### **5.8 Packaging**

Ibrutinib will be prescribed via patient’s preferred pharmacy, as per the appropriate dose schedule.

### **5.9 Blinding of Study Drug**

N/A

### **5.10 Receiving, Storage, Dispensing and Return**

#### **5.10.1 Receipt of Drug Supplies**

Rituximab will be prescribed and dispensed at the infusion clinic at Dartmouth-Hitchcock Norris Cancer Center. Ibrutinib will be prescribed and filled at patient’s preferred pharmacy.

#### **5.10.2 Return or Destruction of Ibrutinib**

At the completion of the study, there will be a final reconciliation of drug received, consumed, and remaining, since our pharmacy may not be shipping drug. Each subject will be asked to bring remaining medications back to our clinic or to dispose of them.

## **6 Study Procedures**

### **Visit 1 (prior to or at the start of therapy)**

Initial visit

1. Initiation of therapy as described above

A subject will be reviewed for:

In order to confirm and assess the extent of GVHD and meet inclusion criteria, this study may require evaluation of participants by utilizing various diagnostic measures (within one week of enrollment):

Medical history

Physical examination, including ht and weight

2. The subject will sign an informed consent
3. Blood Studies
  - baseline CBC/diff, CMP, PT/PTT

-biomarker assays will be drawn

Elisa/Luminex	Flow Cytometry
----------------------	-----------------------

sIL2Ra	CD146
--------	-------

CX3CL1	CCR5
--------	------

CXCL9	
-------	--

CXCL10	
--------	--

CCL22	
-------	--

CCL4	
------	--

ST2	FOXP3
-----	-------

4. Urine studies
  - urinalysis, culture
  - urine for CrCl, as indicated
5. Additional studies, as clinically indicated
6. Studies pertinent to the organ system under consideration for the diagnosis of cGVHD
  - biopsy proven or strong clinical suspicion of a cGVHD diagnosis will be required
7. New pregnancy test
8. New comprehensive infectious work-up with negative findings in the appropriate clinical setting (eg, Pulmonary cGVHD) will be required

The decision to obtain tests and procedures noted above will depend on the individual clinical scenario.

The guidelines for standard cGVHD intervention will be followed

1. Establishment of baseline
 

The degree of cGVHD will be assessed (baseline) prior to initiation of protocol treatment by using chronic graft-versus-host disease assessment and scoring criteria, as referenced in the NIH Consensus Development Project (see Attachments).
2. Treatment initiation
 

Treatment will start once the subject has the ibrutinib pills, on the first day of Rituximab.

